## ANNEX II. Fitness for use assessment

### Data source justification for inclusion and key characteristics

#### **France: Clinical Data Warehouse of Bordeaux University Hospital (CDW Bordeaux)**

CDW Bordeaux will be included in this study because it is a hospital data source that provides relevant information on the use of immunoglobulins in the general population.

Based on a preliminary feasibility assessment, the expected number of person counts for immunoglobulin use in CDW Bordeaux will be 10,900.

Moreover, data availability and follow-up in CDW Bordeaux is sufficient, as data availability starts in 2005, and the date of most recent data extraction is 09/2025, which aligns with the study period. The median follow-up of the first observation period is 247 days.

There are no study specific limitations present in CDW Bordeaux.

Lastly, IRB approval for CDW Bordeaux is estimated to take 1 to 2 weeks, which makes the execution of this study feasible within the current study timelines.

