### Research objectives

The specific objectives of this study are:

1. To estimate the overall and annual prevalence of immunoglobulin use in the general population, overall and stratified by i) type of immunoglobulin, and ii) route of administration. Estimates will be stratified by age and sex.
2. To describe the distribution and quarterly trends of prespecified immunoglobulin brands among prevalent immunoglobulin users (if available).
3. To estimate the number of immunoglobulin prescriptions, treatment duration, and dose (initial, cumulative) of immunoglobulin use during the study period.
4. To characterise patients initiating treatment with prespecified immunoglobulins in terms of i) demographics at index date, ii) indication for use, iii) comorbidities, iv) common infections post-index, and v) antibiotics post-index.

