### 8.3. Study population with inclusion and exclusion criteria

#### *Objective 1*

##### Inclusion criteria

- Present in the data source during the period of 01/01/2017 to 31/12/2024.

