### 8.8.3. Statistical model specification and assumptions of the analytical approach considered

#### Objective 1

Trends of immunoglobulin use during the study period will be assessed based on OMOP CDM mapped data using the *IncidencePrevalence* R package (<https://github.com/darwin-eu/IncidencePrevalence>), developed by DARWIN EU®.

The prevalence of individuals with a recorded immunoglobulin prescription (expressed as the proportion of individuals with any immunoglobulin prescription in the general study population) will be presented by immunoglobulin ingredient, route of administration, and stratified by sex and age.

Prevalence will be calculated as overall and annual, which summarises the total number of individuals with recorded immunoglobulin use during a given period divided by the population at risk of receiving immunoglobulins during that period. Therefore, period prevalence will give the proportion of individuals exposed at any time during a specified interval. Binomial 95% confidence intervals will be calculated.

#### Objective 2

Trends of immunoglobulin use during the study period will be assessed based on OMOP CDM mapped data using the *IncidencePrevalence* R package (<https://github.com/darwin-eu/IncidencePrevalence>), developed by DARWIN EU®.

The quarterly prevalence of individuals with prescriptions for prespecified immunoglobulin brands will be estimated (expressed as the proportion of individuals prescribed each specific immunoglobulin brand among prevalent immunoglobulin users).

Prevalence will be calculated as quarterly period prevalence, which summarises the total number of individuals with recorded immunoglobulin brand prescription during a quarter divided by the population of prevalent immunoglobulin users during that period. Therefore, period prevalence will give the proportion of individuals exposed to a specific brand at any time during the specified interval. Binomial 95% confidence intervals will be calculated.

An illustration of the calculation of period prevalence is shown below in **Figure 3**. Between time  $t+2$  and  $t+3$ , two of the five study participants receive immunoglobulin treatment, giving a prevalence of 40%. Meanwhile, for the period  $t$  to  $t+1$  all five also had some observation time during the year with one of the five study participants having a recorded immunoglobulin prescription, giving a prevalence of 20%.

[figure not shown]

Figure 3. Prevalence example.

### Objective 3

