### Limitations

The study will be informed by routinely collected healthcare data, which introduces several important considerations that may influence the interpretation of the findings.

The study will include data from three European countries. As such, the results reflect only the populations captured within these data sources and may not be generalisable to other countries or healthcare systems.

Electronic health records are primarily designed for clinical purposes rather than research, and as such, may contain incomplete, inconsistent, or variably recorded information. Therefore, the documentation of comorbidities, necessary for patient-level characterisation, may vary across data sources. The actual clinical indication for prescribing immunoglobulins is not directly recorded in the data sources. Instead, proxy measures based on diagnosis codes around the time of the first treatment during the study period are used. Consequently, the estimation of potential indications may be incomplete or imprecise as this might not be recorded in all patients. To minimise incompleteness, different time windows around the immunoglobulin prescription date will be applied to assess the indication of use.

Additionally, a recorded prescription does not guarantee that the medication was dispensed or consumed, therefore assumptions of actual use have been made. Furthermore, the type of health care setting may affect the prevalence of prescriptions of specific immunoglobulin types, e.g., intravenous immunoglobulins are predominantly administered in a hospital setting and not in primary care. The general study population which will be included to estimate the prevalence of immunoglobulin use may also be affected by the type of health care setting and the definition of the observation period by each data source. Primary care data sources generally encompass a broader cohort of individuals, observed from registration until deregistration (CPRD GOLD) or from first to last recorded event (IQVIA DA Germany), while the hospital data source (CDW Bordeaux) comprises individuals requiring inpatient care which are observed from their first to last visit.

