8	Data Harmonization	The data has been mapped to the OMOP CDM v5.4 and the OMOP standard vocabularies (SNOMED, RxNorm, LOINC). The format, structural and semantic conformance has been verified upon onboarding into the DARWIN EU® data network. We use the hospital's unique identifier to generate the patient identifier in OMOP. If two identities are merged at the hospital, the merge is taken into account in the CDW. An automatic (hourly) detection of suspected duplicated identities has been implemented at the hospital since 2020, with merging of duplicated identities by a specialised team. Identities since 2015 were processed retrospectively. Thus, the rate of identity duplication in the database is low, especially since 2015.
9	Quality control (database specific)	- The integrated data comes from the hospital production information system through a real-time replicated database. Consistency evaluations between the replicated database and the production system are performed by the technical team in charge of maintaining the replicated database. - In the same way, consistency checks are performed between the replicated database and the data integrated into the i2b2 CDW. In addition, dashboards enable monitoring the data integrated into the i2B2 CDW, in particular by controlling the amount of data available over time, and its evolution, according to the various data sources. - An internal evaluation was carried out to ensure the consistency between the data integrated

#	Section	Description
		into i2b2 and the data available in the software used at the patient's bedside. In addition, many use cases were performed on the i2b2 CDW, with return to the patient chart and comparison of the data integrated into i2b2 and the data available in the care file.
10	Linkage	Death certificates (without the cause of death).
11	Vital status	The database is linked to the French death registry.
12	Limitations	CDW Bordeaux is limited to events captured in the hospital setting and thus does not include patient events not treated by the hospital (e.g. rare cancers). Patient events that are not included in CDW Bordeaux are rare disease treatments or specialist events that occur outside of CHUBX.
13	Main references	Cossin S, Diouf S, Griffier R, Le Barrois d'Orgeval P, Diallo G, Jouhet V "Linkage of Hospital Records and Death Certificates by a Search Engine and Machine Learning." JAMIA open (2021): 33709061

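### For CDW Bordeaux, objective 1 yields the proportion of one hospital's observed patients with an immunoglobulin record, not general-population prevalence, and Annex II says otherwise

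*Protocol*

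**What the plan says.** **Target.** Protocol Section 7, objective 1: "To estimate the overall and annual prevalence of immunoglobulin use in the general population". Section 8.6.2 defines the outcome for the same population. Table 1 in Section 8.4 lists CDW Bordeaux as contributing to all objectives.

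**Denominator.** The only inclusion criterion for objective 1 in Section 8.3 is "Present in the data source during the period of 01/01/2017 to 31/12/2024", with no exclusions. Section 8.8.3 defines prevalence as the number of users "divided by the population at risk of receiving immunoglobulins during that period".

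**What the source contains.** Section 9: "the hospital data source (CDW Bordeaux) comprises individuals requiring inpatient care which are observed from their first to last visit". Annex I, item 12 for this source: "CDW Bordeaux is limited to events captured in the hospital setting and thus does not include patient events not treated by the hospital".

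**What the fitness assessment claims.** Annex II says that CDW Bordeaux "provides relevant information on the use of immunoglobulins in the general population", and then: "There are no study specific limitations present in CDW Bordeaux".

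**The concern.** The target population and the operational denominator differ by definition. A resident of the Bordeaux area who never attends this hospital is in the general population but not in the denominator. A person treated with immunoglobulin at the hospital enters the denominator through that contact. Section 9 itself notes that intravenous products are given mainly in hospital, so entry to the denominator is tied to the care through which exposure occurs.

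At stake is what may be concluded for France. The planned figures in Section 8.8.4 carry one title for all three sources, annual prevalence of immunoglobulin use per data source, under a research question about use across European countries. A reader who relies on objective 1 and Annex II would take the French curve as population prevalence and could read its height against the German and UK curves as a difference in national use.

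**Working it through.** The protocol states no expected prevalence and no sample size, so there is no planned figure to reproduce. The check sets the passages side by side and then asks whether the difference can be sized.

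**1. What is computed for France.** Combining Sections 8.3 and 8.8.3 with the Section 9 description of the source:

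- Numerator: persons with an immunoglobulin record at this hospital in the period.
- Denominator: persons whose observation, from first to last visit, overlaps the period.

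No catchment or census denominator, standardisation or source-specific label is specified. The denominator is also not limited to patients seen in the year. Someone with visits in 2018 and 2022 and none between counts in 2019, 2020 and 2021.

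**2. Where the text conflicts.**

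| Place | Content for CDW Bordeaux |
|---|---|
| Sections 7 and 8.6.2 | General-population prevalence |
| Annex II | Informs on the general population; no study-specific limitation |
| Section 9 | Hospital patients, first to last visit; uncertain whether users are truly incident; only a subset may contribute to pre-index windows |
| Annex I, item 12 | Only events treated at the hospital |
| Table S1 | Objective 1 study population marked not applicable in every assessment column |

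Section 8.4 refers to Annex II for representativeness, but Annex II does not assess the objective 1 denominator.

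A smaller conflict lies in the source description. Section 9 speaks of persons needing inpatient care, while Annex I, item 4 also includes ambulatory and hospital outpatient care.

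**3. Can the difference be sized?** Let a catchment hold N people and U users. Let s be the share of N under observation in CDW Bordeaux, and c the share of U with a record there. Ignoring patients from outside the catchment:

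hospital-based proportion = cU / (sN) = (c / s) × (U / N).

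The figure exceeds population prevalence when c > s, which is plausible because users are more likely than others to attend. The protocol gives neither c nor s. On the assumption c = 1, shares of s = 10%, 25% and 50% give inflation factors of 1/0.10 = 10, 1/0.25 = 4 and 1/0.50 = 2. With c below 1, because users treated elsewhere are missed, the factor shrinks. N is not defined either: Annex I says that more than 75% of patients live in Gironde and that further cases come from the wider region.

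**4. Crude ratios from the protocol** (Annex II person counts over Table 1 active individuals):

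- CDW Bordeaux: 10,900 / 247,200 = 4.41%
- IQVIA DA Germany: 47,500 / 4,484,200 = 1.06%
- CPRD GOLD: 73,600 / 2,632,700 = 2.80%

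These are not the planned prevalences. The period of the person counts is not stated, while active individuals are those present in the last six months. The two primary care sources differ from each other by 2.80 / 1.06 = 2.6-fold, more than Bordeaux differs from CPRD GOLD (4.41 / 2.80 = 1.6-fold). The ratios therefore do not isolate a hospital-denominator effect.

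**The case against.** The strongest reply is that the protocol already discloses the matter. Section 9 says that results reflect only the populations captured, that the objective 1 population may be affected by care setting and by how observation is defined, and then contrasts the primary care cohorts with the hospital source. Section 8.2, Section 8.8.3 and the mock attrition tables refer to a general study population, so what will be computed is clear. Section 8.9 keeps the sources apart with no meta-analysis, so the German and UK estimates are not contaminated. The mock figure is not reproduced in the text available, so it cannot be shown that the sources share a panel.

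All of this stands, and it makes the point one of a mislabelled estimand and an internal contradiction, not of a hidden flaw. It does not remove the point: Section 9 gives no direction, does not say that no French population prevalence results, and leaves Sections 7 and 8.6.2 and Annex II as they are.

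A second reply is that France is not alone. IQVIA DA Germany is observed from first to last recorded event, with a median first observation period of 116 days against 247 in Bordeaux. Annex I says that CPRD GOLD does not cover hospital and specialist events. Annex II gives both sources the same two sentences. This is fair, and the fix should cover those entries too.

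**Conclusion.** The point holds as a labelling and consistency error with a real consequence. As planned, objective 1 for CDW Bordeaux estimates the proportion of persons under observation in one university hospital's records who have an immunoglobulin record. It is not prevalence in the general population, and the two Annex II sentences contradict Section 9 and Annex I. This rests on definitions in the protocol and needs no numerical assumption.

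A reader might go further and infer that the French figure must exceed any population prevalence, or that the 4.4%, 1.1% and 2.8% ratios measure the distortion. The documents do not support either. Upward is the likely direction, but users treated elsewhere are missing from the numerator, no catchment population is given, and the ratios mix an unstated period with a six-month one. Nor does the protocol conceal the hospital denominator, since Section 9 describes it.

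**What to change.** 1. In Sections 7, 8.6.2 and 8.8.3 and in the output titles of Section 8.8.4, restate the objective 1 estimand for CDW Bordeaux as the proportion of persons under observation in CDW Bordeaux during the period (calendar year, or 2017–2024 overall) with an immunoglobulin record. Do not describe it as patients in hospital contact during the year, unless in-year contact becomes a requirement.
2. State in Section 8.8.3 that no French general-population prevalence will be concluded and that the Bordeaux figure is not to be compared directly with the primary care sources.
3. In the Annex II entry for CDW Bordeaux, replace the general-population sentence and the no-limitation sentence with the limitation described in Section 9.
4. Reconcile the same two sentences for IQVIA DA Germany and CPRD GOLD with Section 9 and, for CPRD GOLD, with Annex I, item 12.
5. Reconcile the inpatient description in Section 9 with the outpatient coverage in Annex I, item 4.

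The cost is wording and labelling. No new data and no change to the computation are needed. The study gives up a French general-population claim that it cannot support.

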#### **Germany: IQVIA Disease Analyzer Germany (IQVIA DA Germany)**

IQVIA DA Germany will be included in this study because it is a primary care data source that provides relevant information on the use of immunoglobulins in the general population.

Based on a preliminary feasibility assessment, the expected number of person counts for immunoglobulin use in IQVIA DA Germany will be 47,500.

Moreover, data availability and follow-up in IQVIA DA Germany is sufficient, as data availability starts in 1989, and the date of most recent data extraction 12/2024, which aligns with the study period. The median follow-up of the first observation period is 116 days.

There are no study specific limitations present in IQVIA DA Germany.

Lastly, IQVIA DA Germany requires no IRB approval, which makes the execution of this study feasible within the current study timelines.

#### **United Kingdom: Clinical Practice Research Datalink GOLD (CPRD GOLD)**

CPRD GOLD will be included in this study because it is a primary care data source that provides relevant information on the use of immunoglobulins in the general population.

Based on a preliminary feasibility assessment, the expected number of person counts for immunoglobulin use in CPRD GOLD will be 73,600.

Moreover, data availability and follow-up in CPRD GOLD is sufficient, as data availability starts in 1987, and the date of most recent data extraction is 05/2025, which aligns with the study period. The median follow-up of the first observation period is 2,150 days.

There are no study specific limitations present in CPRD GOLD.

Lastly, CPRD GOLD has blanket approval, which makes the execution of this study feasible within the current study timelines.

Table S1. Fitness-for-use assessment of data sources.

Design elements	Operational definition	Data elements for valid capture	Criticality of the quality of the element, including justification where relevant	Suggested extensiveness assessment	Suggested assessment of other quality dimensions	Suggested substantiation by documentation
Study population	General study population ( obj. 1 )	N/A	N/A	N/A	N/A	N/A
	Population with an immunoglobulin prescription ( obj. 2–4 )	Prescription of immunoglobulin treatment (RxNorm code)	High	100% will have an immunoglobulin prescription, the expected number of persons counts for immunoglobulins in the data sources included in this study range from 10,900 (CDW Bordeaux) to 73,600 (CPRD GOLD).	100% of prescriptions have been mapped to RxNorm	N/A
Treatment/exposure	Immunoglobulin prescription	Prescription of immunoglobulin treatment (RxNorm code)	High	N/A (to be assessed on a research question basis)	N/A	N/A
Comparator group (not relevant)	N/A	N/A	N/A	N/A	N/A	N/A
Key outcomes per objective	Immunoglobulin prescription ( obj. 1 )	Prescription of prespecified immunoglobulin treatment (RxNorm code), including, if available, route of administration	Medium	Immunoglobulin prescriptions are included in all data sources. The expected number of persons counts for immunoglobulins in the data sources included in this study range from 10,900 (CDW Bordeaux) to 73,600 (CPRD GOLD).	N/A	N/A

Design elements	Operational definition	Data elements for valid capture	Criticality of the quality of the element, including justification where relevant	Suggested extensiveness assessment	Suggested assessment of other quality dimensions	Suggested substantiation by documentation
	Immunoglobulin prescription ( obj. 2 )	Prescription of prespecified immunoglobulin brands (RxNorm code)	Medium	N/A (to be assessed on a research question basis)	N/A	N/A
	Immunoglobulin prescription ( obj. 3 )	Prescription of prespecified immunoglobulin brands (RxNorm code), including treatment duration and dose	Medium	N/A (to be assessed on a research question basis)	N/A	N/A
	Demographic and clinical characteristics ( obj. 4 )	Concept IDs for sex, age, and various clinical characteristics	Medium	N/A (to be assessed on a research question basis)	N/A	N/A
Covariates (including confounders if relevant)	N/A	N/A	N/A	N/A	N/A	N/A
Follow-up time (if relevant)	N/A	N/A	N/A	N/A	N/A	N/A

CDW Bordeaux = Clinical Data Warehouse of Bordeaux University Hospital; CPRD GOLD = Clinical Practice Research Datalink GOLD

EMA Data Quality Framework for EU medicines regulation: application to Real-World Data for more information

([https://www.ema.europa.eu/system/files/documents/other/data-quality-framework-eu-medicines-regulation-application-real-world-data\\_en.pdf](https://www.ema.europa.eu/system/files/documents/other/data-quality-framework-eu-medicines-regulation-application-real-world-data_en.pdf)).

## ANNEX III. Operational and reporting considerations

### DATA MANAGEMENT

#### Data management

All data sources have previously mapped their data to the OMOP common data model. This enables the use of standardised analytics and using DARWIN EU® tools across the network, since the structure of the data and the terminology system is harmonised. The OMOP CDM was developed and maintained by the Observational Health Data Sciences and Informatics (OHDSI) initiative and is described in detail on the wiki page of the CDM: <https://ohdsi.github.io/CommonDataModel> and in The Book of OHDSI: <http://book.ohdsi.org>.

The analytic code for this study will be written in R and will use standardised analytics wherever possible. Each data partner will execute the study code against their data source containing patient-level data and then return the results (csv files), which will only contain aggregated data. The results from each of the contributing data sites will then be combined in tables and figures for the study report.

#### Data storage and protection

For this study, participants from various EU member states will process personal data from individuals that is collected in national/regional electronic health record data sources. Due to the sensitive nature of this personal medical data, it is important to be fully aware of ethical and regulatory aspects and to strive to take all reasonable measures to ensure compliance with ethical and regulatory issues on privacy.

All data sources used in this study are already used for pharmaco-epidemiological research and have a well-developed mechanism to ensure that European and local regulations dealing with ethical use of the data and adequate privacy control are adhered to. In agreement with these regulations, rather than combining person level data and performing only a central analysis, local analyses will be run, which generate non-identifiable aggregate summary results.

The output files are stored in the DARWIN EU® Remote Research Environment (RRE). These output files do not contain any data that allow identification of subjects included in the study. The RRE implements further security measures to ensure a high level of stored data protection to comply with the local implementation of the General Data Protection Regulation (GDPR) (EU) 679/20161 in the various member states.

